## 10.5 TIME PERIOD AND FREQUENCY FOR EVENT ASSESSMENT AND FOLLOW-UP

The occurrence of an UP, AE or SAE may come to the attention of study personnel during study visits and interviews of a study participant presenting for medical care, upon review by a study monitor, or during an audit. All AEs grade 3 or higher but not meeting the criteria for SAEs will be captured on the appropriate CRF. AEs of grade 1 and 2 will not be captured due to the well-characterized side effect profile of BTX for other indications, including endoscopic BTX injection which is FDA approved. Information to be collected includes event description, time of onset, clinician's assessment of severity, seriousness, expectedness, relationship to study product (assessed only by those with the training and authority to make a diagnosis), and date of resolution/stabilization of the event. All AEs grade 3 or higher occurring while on study must be documented appropriately regardless of relationship. All AEs will be followed to adequate resolution.

Any medical condition that is present at the time that the participant is screened will be considered as baseline and not reported as an AE. However, if the study participant's condition deteriorates at any time during the study, it will be recorded as an AE after treatment with study intervention begins.

Changes in the severity of an AE will be documented to allow an assessment of the duration of the event at each level of severity to be performed. AEs characterized as intermittent require documentation of onset and duration of each episode.

At each study visit, the Investigator will inquire about the occurrence of AE/SAEs since the last visit. Events will be followed for outcome information until resolution or stabilization.

The Investigator will record all reportable events with start dates occurring after treatment with study intervention begins for 30 days (for AEs grade 3 or higher) after the intervention is performed or 30 days after date of surgery, whichever is longer. AEs will be evaluated using the current version of the [CTCAE v5.0](#). At each study visit, the investigator will inquire about the occurrence of AE/SAEs since the last visit. Events will be followed for outcome information until resolution or stabilization. Any SAE that occurs after treatment with alternative therapy

will be reported only if the Investigator or current treating physician has assessed the SAE as related to the study treatment.

## 10.6 REPORTING PROCEDURES

### 10.6.1 OHSU IRB REPORTING OF UNANTICIPATED PROBLEMS AND ADVERSE EVENTS

Unanticipated Problems and AEs will be reported to OHSU IRB according to the policies, procedures and guidelines posted on the [OHSU IRB web site](#).

Events that must be reported by the Investigator to the IRB are detailed in the OHSU IRB **Investigator Guidance: Prompt Reporting Requirements (HRP-801)**. Events that meet the criteria for OHSU RNI must be reported to the IRB within 5 days of learning of the event. At a minimum, events requiring reporting to the IRB include:

- Any new or increased risk related to the research, including AEs or IND safety reports that require a change to the protocol or consent,
- New FDA black box warning,
- Publications identifying new risks,
- Data Safety Monitoring Board/Committee letters recommending changes or discussing new risks
- Unanticipated adverse device effect
- Unauthorized disclosure of confidential participant information

### 10.6.2 CENTRAL REPORTING OF ADVERSE EVENTS FOR MULTI-SITE STUDIES

A sub-site must notify the OHSU Coordinating Center of any SAE by phone, fax, or email no later than 24 hours after learning of the event. The sub-site must also report each event to the institution's local IRB or other oversight entity per institutional policies/requirements. The sub-site will send the Coordinating Center supporting materials regarding the SAE, as well as [describe what sub-site must submit to coordinating center, for example: Knight SAE form, MedWatch form 3500, and/or any other trial specific reporting form (AESI, AECI)].

The Coordinating Center will review and submit SAE information to the FDA, OHSU IRB, sub-sites, and any other entities as required by federal and local policies/regulations, and any other applicable requirements.

The Coordinating Center is responsible for distributing IND and/or IDE Action Letters and/or Safety Reports, as applicable, to sub-sites for review and submission to their institution's local IRB as required per site policy.

### 10.6.3 FDA REPORTING

Some events must be reported to the FDA through the MedWatch Voluntary reporting program, even if the trial involves a commercially available agent. Events to be reported include any UPs (i.e., not listed in the package insert) and any SAEs with a suspected association to the study intervention.

For studies conducted under an IND/IDE, the OHSU Coordinating Center Investigator is required to report certain events to the FDA per applicable regulations.

For multi-site investigator-initiated trials, the OHSU PI is the study sponsor and the following reporting responsibilities and requirements apply.

The sub-site investigator is required to report AEs to the Coordinating Center using a MedWatch report form and/or any trial-specific report form and supporting materials. Adverse events to be reported include any UPs (i.e., not listed in the package insert and/or IB) and any SAEs with a suspected association to the investigational product. The Coordinating Center will centrally assess all reported events and report any events to the FDA as warranted using the MedWatch 3500A Mandatory report form.

#### 10.6.4 SUSPECTED UNEXPECTED ADVERSE REACTIONS (SUSARS)

Per regulatory requirements, if an event is assessed by the Sponsor Institution as a Serious Unexpected Adverse Reaction (SUSAR), it is the responsibility of the Sponsor Institution to submit the SUSAR to Regulatory Authorities according to applicable regulations. In addition, the SUSAR will be distributed to the Investigators/sites utilizing a Council for International Organizations of Medical Sciences (CIOMS) report form, or the MedWatch 3500A form). The Investigator/site will submit a copy of the report to their respective IRB or IEC per the governing institutional requirements and in compliance with local laws and guidelines.

#### 10.6.5 REPORTING OF PREGNANCY

To ensure participant safety, each pregnancy or suspected pregnancy in a participant during study participation must be reported within 24 hours of learning of its occurrence. The sub-site investigator is required to notify the OHSU Coordinating Center by phone, fax, or email no later than 24 hours of learning of a pregnancy. The sub-site must also report each event to the institution's local IRB or other oversight entity per institutional policies/requirements. The Coordinating Center will centrally assess the event and report to the manufacturer and any other entity as warranted. The sub-site will send the Coordinating Center information regarding the pregnancy using secure institutional email. Describe what sub-site must submit to Coordinating Center, for example: Knight SAE form template, MedWatch form 3500, and/or any other trial specific reporting form.

The investigator must follow the pregnancy to determine outcome, including spontaneous or voluntary termination, details of the birth, and the presence or absence of any birth defects, congenital abnormalities, or any pregnancy- or childbirth-related and/or newborn complications. The sub-site must report the outcome of the pregnancy to the Coordinating Center as defined above.

If during study participation a participant's sexual partner becomes pregnant, the pregnancy and pregnancy outcomes must also be reported as described above. Consent to report information regarding the pregnancy should be obtained from the pregnant individual.

### 10.7 STUDY STOPPING RULES

The overall study will be paused, and appropriate authorities (e.g., IRB, Knight Data and Safety

Monitoring Committee) notified if the following events occur:

- Life-threatening grade 4 toxicity attributable to protocol therapy that is unmanageable, or unexpected.
- Death suspected to be related to BTX injection.
- As indicated by statistical stopping rules in this protocol per Section 11.4.5: 1) During safety run-in if two or more out of the first six participants experience a surgical delay  $\geq$  14 days past the previously scheduled date. 2) Interim analysis if two or more of the first 25 participants experience crPOPF. If either of these events are met the trial will be stopped. In the case of the safety run-in, the trial may be resumed if a correctable cause for the serious adverse events can be found or a prophylactic treatment administered.

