## SCHEMATIC OF STUDY DESIGN

Procedure	BTX Injection		Surgery and Postoperative Period				
	Day 1	Day 7-14 (Pre-operative Medicine Appointment)*	Day 1 (Day of Surgery)	Day 4 (Postoperative Day 3)	Day of Discharge	Discharge + 7-14 Days (Post-Operative Follow-up)	Day 30
Physical exam	X		X*	X*	X*	X*	
Vital signs 	X	X*	X*	X*	X*	X*	
ECG (if indicated)		X*	X*				
Routine blood draw  (1 tablespoon)		X*	X*	X*			
Drain Fluid Analysis				X*			
Pregnancy test (if indicated)	X	X*	X*				
Review any adverse events		X	X				X
Review all other medications	X	X	X				
BTX Injection	X						
Distal Pancreas Resection			X*	X*			
IN THE EVENT OF OPERATIVE DELAYS, PATIENTS STILL EVALUABLE FOR EFFICACY IF RECEIVING SURGERY UP TO 28 DAYS FROM BTX INJECTION. A PRE-OPERATIVE MEDICINE APPOINTMENT PRIOR TO BTX INJECTION IS GENERALLY NOT NEEDED, BUT MAY BE REQUESTED FOR SOME PATIENTS DEPENDING ON HEALTH STATUS AND CLINICIAN DISCRETION							

\* Interventions/monitoring per standard of care

 Can include heart rate, blood pressure, height, weight, oxygen saturation, temperature

 Can include CBC with differential, chemistry, magnesium, uric acid

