## 1.3 RISK/BENEFIT ASSESSMENT

### 1.3.1 KNOWN POTENTIAL RISKS

Botulinum toxin (onabotulinumtoxinA; Botox) has been used for decades with great efficacy in multiple conditions. BTX has an excellent safety profile, with one systemic review of 36 randomized controlled trials noting no serious adverse events, with focal weakness at/around the injection site being the only mild-moderate adverse event that occurred more often than controls, which is not a relevant risk for endoscopic injection. Post-marketing reports indicate that the effects of all botulinum toxin products may spread from the area of injection to produce symptoms consistent with botulinum toxin effects. These may include asthenia, generalized muscle weakness, diplopia, ptosis, dysphagia, dysphonia, dysarthria, urinary incontinence and breathing difficulties, depending on the site of injection. These symptoms have been reported hours to weeks after injection. Swallowing and breathing difficulties can be life threatening and there have been reports of death. The risk of symptoms is probably greatest in children treated for spasticity but symptoms can also occur in adults treated for spasticity and other conditions, particularly in those patients who have underlying conditions that would predispose them to these symptoms. In unapproved uses, including spasticity in children, and in approved indications, cases of spread of effect have been reported at doses comparable to those used to treat cervical dystonia and at lower doses.

In cases of endoscopic BTX injection, side-effects apart from asymptomatic serum lipase elevations or mild pancreatitis have not been previously reported when administered for Sphincter of Oddi dysfunction, post-cholecystectomy biliary pain, or for prevention of POPF.

Risks specific to endoscopy represent additional study-related risks, and include postinterventional pancreatitis defined by the Atlanta criteria which includes two of the following: 1) abdominal pain consistent with acute pancreatitis; 2) serum lipase  $> 3$  ULN; 3) characteristic imaging findings). Rare risks with the upper endoscopy procedure include cardiopulmonary compromise with procedural sedation, intraprocedural hemorrhage, and bowel perforation.

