#### 11.4.5 PLANNED INTERIM ANALYSES AND STOPPING RULE

A safety-run in to test the endoscopic BTX injection technique will be performed. During the safety run-in, the PI will evaluate patient safety outcomes including grade 3 or higher adverse events. Additionally, the study will be evaluated by the DSMC following the completion of the first three participant's safety evaluation periods (30 days following BTX injection or 30 days following surgery, whichever is longer). Progressive study enrollment will continue throughout the safety run-in, and enrollment will be halted if recommended by the DSMC after completion of the run-in. If 2 or more of the first 6 participants enrolled experience delay in planned surgery  $\geq$  14 days (due to significant GI hemorrhage, perforation, or adverse reaction to BTX) or pancreatitis requiring hospitalization, then the study will be halted for safety. If 2 or more of the first 6 participants experience delay in planned surgery  $\geq$  14 days (due to significant GI hemorrhage, perforation, or adverse reaction to BTX) or pancreatitis requiring hospitalization, the study will be halted for safety. An analysis of adverse events will be performed, and if an alteration in the intervention technique or other prophylactic treatment cannot be identified the study will be terminated. If an alteration or prophylactic treatment can be found, the study will resume with an additional 6 patient safety run-in with identical stopping rules.

A futility analysis will be conducted based on the stopping rule of Simon's two-stage design after 25 Stage I participants have met the eligibility criteria for the efficacy evaluable population (defined in 11.3.2). All participants enrolled on stage 1 (n=25) will need to complete the study intervention, distal pancreas resection, and 30 days of follow up for postoperative pancreatic fistula before the interim analysis can be completed. Recruitment will be paused until interim analysis is completed. The trial will be terminated if there are 2 or more crPOPF among these 25 participants. If there are less than 2 crCOPF among these Stage I participants, the trial will continue and enroll 25 additional participants in Stage II. The treatment will be considered promising and deserving of further investigation if there are less than 3 crCOPF among the total of evaluable 50 participants.

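### Section 10.7 restates the safety run-in rule of Section 11.4.5 incorrectly: it leaves out hospitalized pancreatitis, the causes of delay that count, and the terms for resuming

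*Combined protocol and SAP*

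**What the plan says.** Three sections of the combined protocol and SAP describe the safety run-in.

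- **Sections 3.1 and 11.4.5** halt the study if at least two of the first six participants have a surgical delay of 14 days or more "due to significant GI hemorrhage, perforation, or adverse reaction to BTX) or pancreatitis requiring hospitalization". Section 11.4.5 states this twice and 3.1 once, with the same content.
- **Section 11.4.5** alone says what follows a halt. Adverse events are analyzed, and "if an alteration in the intervention technique or other prophylactic treatment cannot be identified the study will be terminated". If a change is found, "the study will resume with an additional 6 patient safety run-in with identical stopping rules".
- **Section 10.7**, headed Study Stopping Rules, introduces its version with "As indicated by statistical stopping rules in this protocol per Section 11.4.5". The trigger it then gives is "During safety run-in if two or more out of the first six participants experience a surgical delay" of at least 14 days beyond the date previously set. On restarting, it says that "the trial may be resumed if a correctable cause for the serious adverse events can be found or a prophylactic treatment administered".

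All of this is current text.

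**The concern.** Section 10.7 carries the title under which study staff, the IRB and the monitoring committee would look for the halting criteria. If its short form differs from the rule it claims to apply, someone who works from 10.7 alone can reach a different safety decision from someone who works from 11.4.5.

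The omitted trigger has substance. For endoscopic BTX injection, Section 1.3.1 says that "side-effects apart from asymptomatic serum lipase elevations or mild pancreatitis have not been previously reported". Pancreatitis with admission opens the list in the secondary safety endpoint (Section 2.2) and is a named SAE (Section 10.2.2). Enrollment continues during the run-in, so the count has to be right as events occur. The resumption terms matter as well: 11.4.5 tests a modified technique in six further participants before the trial goes on, and 10.7 does not mention that step.

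**Working it through.** The plan states no operating characteristics for the run-in rule, so there is no figure to reproduce. The main check is a comparison of texts.

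| Element | 3.1 and 11.4.5 | 10.7 |
|---|---|---|
| Threshold | 2 or more of first 6 | 2 or more of first 6 |
| Delay of 14 days or more | counts if due to GI hemorrhage, perforation or a reaction to BTX | counts; no cause given |
| Pancreatitis with admission | counts on its own | not listed |
| No remedy found | study terminates (11.4.5 only) | not stated |
| Remedy found | new 6-patient run-in, same rules (11.4.5 only) | may resume; no run-in mentioned |

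**Is pancreatitis a separate trigger?** Yes. In "due to significant GI hemorrhage, perforation, or adverse reaction to BTX) or pancreatitis requiring hospitalization" the parenthesis holding the causes of delay closes before pancreatitis is named. Pancreatitis is therefore an alternative to delay, not a fourth cause of it.

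**Where the two wordings give different decisions**

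1. Two participants are admitted with pancreatitis and neither has a 14-day delay. Under 3.1 and 11.4.5 the count is 2 and the trial halts. Under 10.7 the count is 0 and it continues.
2. One participant has such an admission and another has a 14-day delay from hemorrhage. The counts are 2 and 1, so again only 3.1 and 11.4.5 halt.
3. Two participants have pancreatitis that delays surgery by 14 days or more. Both wordings count 2 and there is no difference.

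The missed halt is thus confined to pancreatitis admissions without a long delay.

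**Do the other pauses in 10.7 cover cases 1 and 2?** Usually not. They need a death suspected to be related to BTX injection, or a life-threatening grade 4 toxicity that is unmanageable or unexpected. The fallback scale in 10.2.4 puts an event that needs admission but is not immediately life-threatening at grade 3. Pancreatitis is also anticipated in 1.3.1 and has a management plan in 7.4.4.

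**Size, by assumption only.** Let p be the chance that a participant has a pancreatitis admission without a 14-day delay, and suppose no other trigger event occurs. The rule in 11.4.5 then halts with probability

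P(X ≥ 2) = 1 − (1 − p)^6 − 6p(1 − p)^5, with X ~ Binomial(6, p),

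and literal 10.7 never halts.

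| p | 11.4.5 halts |
|---|---|
| 0.000233 (17/73,029, Table 3) | 8.1 × 10⁻⁷ |
| 0.02 | 0.6% |
| 0.05 | 3.3% |
| 0.10 | 11.4% |
| 0.20 | 34.5% |

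For p = 0.10: 1 − 0.5314 − 0.3543 = 0.1143. Only the first row uses a rate from the documents, and that rate covers endoscopy in general, not injection at the papilla. The other values of p are assumed, and nothing in the documents favors one over another.

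The same formula shows what the second run-in is for. If the event rate after a change were still 20% or 30% (assumed), it would halt again with probability 34.5% or 58.0%.

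**The case against.** The strongest defense is that the correct rule can be recovered. Section 10.7 points to 11.4.5, the full rule appears three times elsewhere in agreement, and 10.7 sets up no rival rule on purpose. During the run-in the PI reviews adverse events of grade 3 or higher, and the DSMC reviews the study after the first three participants' safety periods and can recommend a halt. Two admissions for pancreatitis would be reported as SAEs and would not go unseen. All of this stands and limits the harm. It does not put the missing trigger back into 10.7, because those reviews are a matter of judgment whereas the 2-of-6 rule is not.

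Some stronger readings are tempting but not supported:

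- **Ordinary scheduling delays would stop the trial.** A reader might infer this because 10.7 names no cause, and because the schematic foresees delays: "PATIENTS STILL EVALUABLE FOR EFFICACY IF RECEIVING SURGERY UP TO 28 DAYS FROM BTX INJECTION". But the resumption sentence in 10.7, "the trial may be resumed if a correctable cause for the serious adverse events can be found or a prophylactic treatment administered", treats the triggering events as adverse events, and 10.2.2 lists procedure-related complications that delay surgery as SAEs. Delays caused by complications were probably meant. The evaluability window says nothing about how often unrelated delays occur.
- **10.7 contradicts 11.4.5 on resumption.** Its wording is permissive and can stand alongside the extra conditions in 11.4.5. It is an omission. Section 3.1 also gives no resumption terms.
- **10.7 misses the only known complication of the procedure.** Section 1.3.1 also lists hemorrhage, perforation and cardiopulmonary compromise as endoscopy risks. For BTX injection it reports only mild pancreatitis, not cases needing admission.
- **A missed halt is likely.** The larger probabilities in the table need event rates that no section supports.

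**Conclusion.** Wrong as written. Section 10.7 attributes its run-in rule to 11.4.5 but omits hospitalized pancreatitis as a stand-alone trigger, the list of causes that qualify a delay, and the terms for termination or a repeat run-in. The first omission can reverse a halt decision. The second leaves an ambiguity that the mention of serious adverse events partly resolves. The third is silence on a required step.

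The conclusion rests on the text alone and needs no assumed rate. Its practical size cannot be estimated from the documents, and it arises only if someone applies 10.7 literally without going to 11.4.5. The threshold is the same in every section, and the two-stage efficacy design is not affected.

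**What to change.** Replace the run-in trigger and resumption text in 10.7 with the rule in 11.4.5:

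- Halt if two or more of the first six participants have either a surgical delay of at least 14 days due to significant GI hemorrhage, perforation or an adverse reaction to BTX, or pancreatitis that requires hospitalization.
- Terminate if no alteration of technique and no prophylaxis can be identified.
- Otherwise resume with a further six-patient run-in under the same rules.

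Sections 3.1 and 11.4.5 need no change for this purpose. The correction should not bring in new rules, for example on sedation-related delays or cancelled surgery. The documents contain none, and a sedation clause would not match the three causes in the retained list.

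The cost is one wording correction, taken through the CRRC and IRB approval that Section 14.5 requires for any modification. No new data are needed: hospitalized pancreatitis is already an SAE under 10.2.2, and Section 8.5 already records reasons for a delayed or cancelled operation.

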## 11. STATISTICAL CONSIDERATIONS

### 11.1 STATISTICAL HYPOTHESIS

This study is a Phase II, open-label study to determine the effect of pre-operative endoscopic BTX injection on crPOPF rates following distal pancreatectomy. It is hypothesized that the rate of crPOPF in study participants will be significantly lower than the known historical rate of crPOPF.

